1.2. Rationale for the Study

The research data available to date indicate that SCB01A is a promising anti-cancer agent with vascular disrupting activity that has potential for treatment of various malignancies, particularly for patients with drug resistance to existing therapies. The drug has been trialed in human subjects in dose-escalation phase I study, and maximum tolerated dose (MTD) is 24 mg/m² (each cycle consists of one intravenous [i.v.] administration of SCB01A via a central line every 3 weeks). In the phase I study, partial response (PR) (shrinkage of tumor size to 50%) was observed in cycle 9 (3 mg/m²) of one subject with right buccal squamous cell carcinoma and disease stabilization lasted for 14 cycles. Summary from current clinical findings note a total of 19/33 (57.6%) subjects had stable disease (SD) for at least 2 cycles. Extended disease stabilizations were especially observed for 23 cycles in one subject with cholangiocarcinoma (4 mg/m²) and 15 cycles in one subject with rectal cancer (3 mg/m²) respectively, suggested that the most prominent SD subjects remain in low dose (less than 6.5 mg/m²).

Pre-clinical study of SCB01A showed that the concentrations at which tubulin inhibition occurred were around 80 nM for 24-hour exposure or 200 nM for 6-hour exposure. However, pharmacokinetic (PK) results of both phase I study and an ongoing phase II study showed that the average elimination half-life (t_{1/2}) of a 3-hours i.v. infusion of SCB01A is approximately 2.5 hours and almost no SCB01A can be detected after 10 hours, indicating most subjects were treated in short API exposure time and may have been insufficient to achieve efficacy. Furthermore, clinical experiences demonstrated that extended infusion duration may reduce susceptible chemotherapy induced adverse reaction especially peripheral neuropathy (JCO 1999, 17(11): 3403-11). Summary from both efficacy and safety evidences suggesting that to extend the cumulative exposure duration of SCB01A beyond effective concentration in blood may be benefit to patient's best interest.

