Two phase I clinical studies were performed "A Phase 1 Dose Escalation Study of SCB01A in Subjects with Advanced Solid Tumors Who Have Failed Standard Therapy" and "Long-Term Compassionate Use Study for Continued Administration of SCB01A in Subjects Who Completed Treatment With SCB01A in the Previous Protocol #SCB01A-01" respectively. The phase I study demonstrated that SCB01A has encouraging safety and efficacy and support for further Phase II study. 33 subjects were enrolled in the study and 31 subjects completed the main treatment. Among the 31 subjects, 11 of them completed the extension treatment of SCB01A. Up to date, 5 subjects, two in main and extension period respectively, experienced 7 SUSAR events. (Including gastric ulcer bleeding, thrombocytopenia, cough, radiation recall dermatitis, thromboembolic event, muscle weakness lower limb, and sepsis). In addition, 5 dose limiting toxicities and 61 adverse reactions were reported in this study.

The aim of this Phase II study with SCB01A is to determine the efficacy and safety of SCB01A in subjects with squamous cell carcinoma of head and neck who have failed previous platinum based therapies.

2. Study Objectives

This is a Phase II study with intra-subject dose escalation to evaluate the efficacy and safety of SCB01A in subjects with recurrent or metastatic squamous cell carcinoma in head and neck.

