End of study will be either 12 months after the 1st treatment with SCB01A or end of 27 weeks survival follow-up, whichever comes later.

Data and Safety Monitoring Board (DSMB)

The responsibilities of the DSMB, composed of medical monitors (physicians experienced in oncology studies) and at least one statistician, are to review and evaluate the data for safety, study conduct and progress, and make recommendations concerning the continuation, modification, or termination of study. Serial assessments of PK results also may be taken into account for safety evaluation. A neurologist will be invited to join DSMB meeting as a consultant when neurotoxicity occurred.

The document review or meeting of DSMB will be held when the following scenarios:

- A subject is not recovered from Grade 2 neurotoxicity over three weeks;
- A subject revealed Grade 3 or above neurotoxicity;
- After 10 evaluable subjects finished the study in Stage I;

The schedule of assessments is shown in detail in [Table 1](#), [Table 2](#) and [Table 3](#). The results of protocol specific assessments and procedures will be recorded in the source documents for the subjects and on the appropriate page of the case report form (CRF). The different study days are described below.

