6.2. Dose Limiting Toxicity (DLT)

All toxicities will be classified according to the NCI Common Terminology Criteria for AEs (CTCAE) version 4.03.

DLT will be defined as the occurrence of any of the following criteria unless there is definitive alternative evidence that administration of SCB01A did not cause the specific toxicity:

- Grade 4 neutropenia exceeding 5 days' duration
- Grade 4 thrombocytopenia
- Grade 4 anemia
- Grade 3 or greater neutropenia with complications (e.g., fever, infection etc.)

- Grade 3 or greater thrombocytopenia with complications (e.g., bleeding)
- Grade 3 or greater non-hematological AEs including Grade 3 unmanageable nausea and vomiting that persist for 3 or more days after drug administration. Grade 3 fatigue lasting for ≤ 1 week is not considered as a DLT
- Grade 3 or greater prolonged QTc interval
- Grade 3 or greater neurotoxicity
- Delayed treatment exceeding 14 days duration due to drug-related toxicity.
- Not able to recover from grade 2 neurotoxicity exceeding 3 weeks

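### No non-neurological toxicity, cumulative DLT count or drug-related death is a listed trigger for DSMB review, and no general safety look is listed during Stage II

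*Protocol*

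**What the plan says.** Protocol section 3.1 gives the DSMB a broad remit. On that text its duties "are to review and evaluate the data for safety, study conduct and progress, and make recommendations concerning the continuation, modification, or termination of study". A list of the occasions on which it acts comes next, and it has three items:

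- Milder neurotoxicity that lasts is the first: "A subject is not recovered from Grade 2 neurotoxicity over three weeks".
- Severe neurotoxicity in any one person is the second: "A subject revealed Grade 3 or above neurotoxicity".
- A milestone, not an event, is the third: "After 10 evaluable subjects finished the study in Stage I".

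The synopsis carries the same three items. Neither place has an item for other safety concerns, a periodic review or a review during Stage II. The SAP text does not mention the DSMB.

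Section 1.2 reports seven phase I SUSAR events in five subjects: "gastric ulcer bleeding, thrombocytopenia, cough, radiation recall dermatitis, thromboembolic event, muscle weakness lower limb, and sepsis". It also reports five DLTs in that 33-subject study, and says of the once-per-3-week schedule that the "maximum tolerated dose (MTD) is 24 mg/m²".

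**The concern.** The listed occasions are much narrower than the remit. The two event-driven triggers cover one organ system. The third comes only when Stage I is complete.

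Most of the toxicity the protocol itself treats as important lies outside the two neurotoxicity triggers. That holds for most of the phase I SUSARs and for most of the DLT criteria in section 6.2.

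The rules that do respond to a non-neurological DLT act on one subject at a time: dose reduction in section 3.1, and a treatment hold or cessation in section 4.9. If several early subjects had serious non-neurological DLTs, or one died of a drug-related cause, the plan followed as written would go on enrolling and escalating. The body charged with advising on continuation would not be called.

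**Working it through.** **1. Subjects treated before the general look.** The plan's own figures reproduce with the stated 20% dropout. Stage I is 10/(1 − 0.20) = 12.5, rounded up to 13. Stage II is 19/0.80 = 23.75, rounded up to 24. The total is 29/0.80 = 36.25, rounded up to 37. So 10 to 13 subjects may be treated before the Stage I look, and 19 to 24 more in Stage II with only the neurotoxicity triggers in force.

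**2. What the neurotoxicity triggers miss.**

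- *SUSARs (section 1.2).* Gastric ulcer bleeding, thrombocytopenia, thromboembolic event and sepsis are 4 of 7 (57%). Adding cough and radiation recall dermatitis gives 6 of 7 (86%). Lower-limb muscle weakness is the only one that might count as neurological.
- *DLT criteria (section 6.2).* There are ten, and two name neurotoxicity. Two more, Grade 3 or greater non-haematological events and treatment delay over 14 days, could be met by neurotoxicity or by something else. The other six (five haematological, one QTc) are not neurotoxicity.

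**3. Exposure per cycle.** There are two infusions per 21-day cycle.

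| Cycle | Dose per cycle (mg/m²) | Relative to 24 mg/m² once per cycle |
|---|---|---|
| 1 | 2 × 12 = 24 | 1.0 |
| 2 | 2 × 18 = 36 | 1.5 |
| 3 | 2 × 24 = 48 | 2.0 |

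The infusion here lasts 24 hours, while the phase I PK results in section 1.2 are for a 3-hour infusion. The ratios are therefore not a measure of toxicity. They show only that phase I tolerability does not carry over directly, so review across subjects matters.

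**4. Expected DLTs in Stage I.** Expected number = 13 × rate. The rates are assumptions. The lowest is close to phase I, where 5/33 = 15.2% is an upper limit on the share of subjects with a DLT, since one subject may have had more than one.

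| Assumed DLT rate | Expected among 13 |
|---|---|
| 15% | 1.95, about 2.0 |
| 30% | 3.9 |
| 40% | 5.2 |
| 50% | 6.5 |

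**5. What a cross-subject trigger could do.** For illustration only, take a bound that calls a document review when the cumulative number of subjects with any DLT reaches 3 within the first 3–5 subjects, 4 within 6–8, 5 within 9–11, or 6 within 12–13. Let P(k, n) be the probability of k DLT subjects among n with the bound not yet reached. Then P(k, n) = p·P(k − 1, n − 1) + (1 − p)·P(k, n − 1) for k below the bound at n. The firing probability is 1 minus the sum of P(k, 13) over k.

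| True DLT rate | Probability of a review by subject 13 |
|---|---|
| 15% | 4% |
| 20% | 10% |
| 30% | 31% |
| 40% | 58% |
| 50% | 81% |

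At 50%, the mean subject number at firing is 6.0 among trials in which the bound fires. Counting non-firing trials as 13 gives 6.0 × 0.807 + 13 × 0.193 = 7.4. This assumes each subject's DLT status is known in order of entry. Escalation runs over three cycles, so in practice some DLTs would appear later.

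**The case against.** The strongest reply is that oversight does not rest on the trigger list alone. SAEs reach the sponsor or CRO within 24 hours (section 7.4). Every adverse event causing permanent withdrawal is discussed with the medical monitor (section 7.2), and the board is itself made up of medical monitors with at least one statistician. The sponsor may stop the study for medical, ethical or safety reasons (sections 3.8.1 and 9.6). All of this is true. But none of these provisions convenes the board or applies a rule across subjects.

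Several stronger readings are tempting, and the documents do not support them:

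- *That non-neurological events cannot reach the board.* They are not listed triggers. The remit is general, and an unscheduled review is not forbidden.
- *That the board sees nothing before the end of Stage I.* One Grade 3 neurotoxicity would convene it.
- *That drug-related deaths were among the phase I SUSARs.* None is listed.
- *That toxicity withdrawals do not advance the evaluable count.* Under the synopsis, a subject withdrawn for a DLT counts as per-protocol, and section 3.1 exempts study-drug toxicity from non-evaluability. Only those who leave early for other reasons are replaced.
- *That the doses are wrong or wholly untested.* No single planned infusion exceeds 24 mg/m², and section 4.7 bases the doses partly on ongoing phase II studies whose schedules are not described in full.

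The numerical bound has no source in the documents. It counts DLTs of any type, including neurotoxic ones that may already prompt a review. These are fair limits on the illustration, but they do not close the gap.

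**Conclusion.** The point holds as a gap in a stated safety rule and should be fixed. No listed trigger brings a non-neurological DLT, an accumulation of DLTs or a drug-related death to the DSMB before the end of Stage I. None does so at any time in Stage II.

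The size depends on the true DLT rate, which is unknown for this regimen. Over assumed rates of 15% to 50%, between 2.0 and 6.5 of 13 Stage I subjects would have a DLT. If these were non-neurological, none would by itself convene the board before the Stage I look. If some were neurotoxic, the board could meet sooner.

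The textual finding is firm. The firing probabilities are exact for the bound shown, but that bound is only an example. No sample-size or response-rate figure is affected.

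**What to change.** Add two document-review triggers to the DSMB list in both the synopsis and section 3.1:

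1. Any death assessed as possibly, probably or definitely related to SCB01A, using the causality categories already in section 7.1.2.
2. A cumulative count of subjects with any DLT reaching a tabulated bound. Count treated subjects, not evaluable ones, so that replaced subjects still contribute.

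Both should apply through Stages I and II. The sponsor and the DSMB should set the bound in advance and state its firing probabilities over a range of DLT rates. The illustrative bound stops at 13 subjects, so it would have to be extended to cover up to 37.

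The cost is one protocol paragraph and a small table. The board, the document-review format and the DLT and SAE data already exist. The downside is an occasional unneeded review: with the illustrative bound, a 4% chance by subject 13 at a true rate of 15%, or 10% at 20%. The change prescribes no dose, treatment or stopping rule. It only settles when the board is asked to look.

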3.2. Screening and Treatment Phase

3.2.1. Screening Evaluations

The following procedures/assessments will be performed during the screening visit, which will be performed within 28 days prior to Day 1 of Cycle 1:

- Written informed consent
- Initial history and pre-existing conditions (including all prior anti-tumoral therapy, surgery or radiotherapy related to Head and Neck cancer)
- Review of inclusion and exclusion criteria
- Physical examination
- Vital signs
- Eastern Cooperative Oncology Group (ECOG) performance status
- Concomitant medication
- 12-lead ECG
- Radiological imaging according to RECIST v1.1
- Laboratory tests (hematology, clinical chemistry, coagulation and serum pregnancy test)
- Urinalysis
- Nerve Conduction Velocity

3.2.2. Cycle 1, Day 1 (C1D1)

The following procedures/assessments will be performed:

Pre-treatment

- Record pre-existing conditions (baseline signs and symptoms with an onset between time of signing the informed consent and the first dose of study drug)
- Physical examination
- Vital signs
- Calculation of body surface area (BSA)
- ECOG performance status
- Concomitant medication
- 12-lead ECG
- Laboratory tests (hematology*, clinical chemistry* and coagulation)
- Urinalysis*

*Test results within 2 days are acceptable, only items not performed for screening within 2 days before this visit need to be tested again.

Study Drug Administration

- Study treatment - i.v. infusion for 24-hour of SCB01A

Post-initiation of Study Drug Administration

- Vital signs
- AEs
- Concomitant medication
- 12-lead ECG - *At 10 and 24 hours after the start of infusion*

3.2.3. Cycle 1, Day 8 (C1D8) \pm 1 day

The following assessments will be performed:

- Physical examination
- Vital signs
- Calculation of BSA
- ECOG performance status
- AEs
- Concomitant medication
- 12-lead ECG - *At pre-infusion, 10 and 24 hours after the start of infusion*
- Laboratory tests (hematology, clinical chemistry and coagulation)
- Study treatment infusion

3.2.4. Cycle 1, Day 15 (C1D15) \pm 2 days

The following assessments will be performed:

- Physical examination
- Vital signs
- ECOG performance status
- AEs
- Concomitant medication
- Laboratory tests (hematology, clinical chemistry and coagulation)

3.2.5. Cycle 2, Day 1 (C2D1) \pm 1 day

The following assessments will be performed:

- Physical examination
- Vital signs

- Calculation of BSA
- ECOG performance status
- AEs
- Concomitant medication
- 12-lead ECG - *At pre-infusion, 10 and 24 hours after the start of infusion*
- Laboratory tests (hematology, clinical chemistry and coagulation)
- Urinalysis
- Study treatment infusion

3.2.6. Cycle 2, Day 8 (C2D8) ±1 day

The assessments on Day 8 of Cycle 2 is identical to Cycle 1, Day 8 (see [Section 3.2.3](#))

3.2.7. Cycle 2, Day 15 (C2D15) ±2 days

The assessments on Day 15 of Cycle 2 is identical to Cycle 1, Day 15 (see [Section 3.2.4](#))

3.2.8. Cycle 3, Day 1 (C3D1) ±1 day

The assessments on Day 1 of Cycle 3 are identical to Cycle 2, Day 1 (see [Section 3.2.5](#)) with the exception of extra PK sampling if dose level of Cycle 3 is 24mg/m² - At pre-infusion, 24, 25, 26, 28, and 32 hours after the start of infusion.

3.2.9. Cycle 3, Day 8 (C3D8) ±1 day

The assessments on Day 8 of Cycle 3 is identical to Cycle 1, Day 8 and Cycle 2, Day 8 (see [Section 3.2.3](#) and [3.2.6](#)) with the exception of extra PK sampling if dose level of Cycle 3 is 24mg/m² - At pre-infusion, 24, 25, 26, 28, and 32 hours after the start of infusion.

3.2.10. Cycle 3, Day 15 (C3D15) ±2 days

The assessments on Day 15 of Cycle 3 are identical to Cycle 1, Day 15 and Cycle 2, Day 15 (see [Section 3.2.4](#) and [3.2.7](#)).

3.2.11. Cycle 4, Days 1 and 8 (C4D1 and C4D8)

If the subject, per the investigator's discretion, is experiencing clinical benefit, they may continue with treatment of SCB01A at the same dose until the study is terminated. The assessments on Days 1 and 8 will continue to be the same as for Cycle 2, Day 1 and Day 8 (see [Section 3.2.5](#) and [3.2.6](#), respectively) with the exception that ECG will only be performed prior to study drug administration (pre-infusion, 0 hr), and then at the end of the infusion (24 hr) on Days 1 and 8 of additional treatment cycles beyond Cycle 3.

Tumor assessment should be performed at baseline, and at the end of every 3 cycles which needs to be arranged within 4 days prior to the next cycle.

Note: No Day 15 visit starting from Cycle 4.

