3.1. Description of Overall Study Design and Plan

[figure not shown]
This study is a multicenter, open-label, Phase II trial. The study will be conducted in two stages:

- **Stage I:** A total of up to 10 evaluable subjects will be enrolled for Stage I to receive at least 3 cycles of i.v. administration by 24-hours infusion of SCB01A under intra-subject dose escalation regimen. The tumor response review will be performed with the subjects who completed at least 3 cycles of SCB01A treatment. If at least one response (CR or PR) is observed, another 19 evaluable subjects will be enrolled into Stage II.
- **Stage II:** 19 evaluable subjects will be enrolled at stage II and treated with the same intra-subject dose escalation regimen from starting dose 12 mg/m². The tumor response review will be performed with the subjects who completed 3 cycles of SCB01A treatment.

Intra-Subject Dose Escalation

All subjects enrolled in this study will be treated from the same starting dose 12 mg/m² (Dose 1) given on Days 1 and 8 in a 21-day cycle by 24 h IV infusion. If the subject experiences no dose-limiting toxicity (DLT) during the period, dose escalation of SCB01A to 18 mg/m² (Dose 2) occurred from cycle 2; and increased to 24 mg/m² (Dose 3) on cycle 3 ([Figure 1](#)).

Figure 1: Intra-Subject Dose Escalation Plan

[figure not shown]
Dose Modification

If the subject experiences a DLT at a given dose level, dose escalation will be halted and a reduced dose will be given to the subject. Dose adjustments were allowed based on the toxicity, efficacy evaluation, and clinical judgment by physician.

Rules for dose modifications of the study ([Figure 2](#)) are listed as following:

1. Dose 1 (12 mg/m²), will be the starting dose regimen for all subjects. Safety and clinical benefit observation will be performed prior to drug administration on Cycle 2 Day 1.
 - a) Dose de-escalation: if any DLT experienced before Cycle 1 Day 8, the dose will be de-escalated to Dose 1a (9 mg/m²) for Cycle 1 Day 8. If first DLT during Cycle 1 is experienced after Cycle 1 Day 8, the dose will be de-escalated to Dose 1a (9 mg/m²) for Cycle 2. If no DLT is observed in Dose 1a, the subjects will receive the Dose 1a until PD, consent withdraw or death.

- Once more dose de-escalation (Dose 1b, 7 mg/m²) will be allowed if another DLT is observed in Dose 1a.

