- b) Dose maintained: If clinical benefit observed at Dose 1 and without DLT, the dose level can be maintained until PD, intolerable toxicity, consent withdraw or death.
2. Dose 2 (18 mg/m²), will be administrated for one cycle and safety and clinical benefit observation will be performed prior to drug administration on Cycle 3 Day 1.
- a) Dose de-escalation: if any DLT experienced before Cycle 2 Day 8, the dose will be de-escalated to Dose 2a (15 mg/m²) for Cycle 2 Day 8. If first DLT during Cycle 2 is experienced after Cycle 2 Day 8, the dose will be de-escalated to Dose 2a (15 mg/m²) for Cycle 3. If no DLT is observed in Dose 2a, the subjects will receive the Dose 2a until PD, consent withdraw or death. Once more dose de-escalation (Dose 2b, 12 mg/m²) will be allowed if another DLT is observed in Dose 2a.
- b) Dose maintained: If clinical benefit observed at Dose 2 and without DLT, the Dose 2 can be continued until PD, intolerable toxicity, consent withdraw or death.
3. Dose 3 (24 mg/m²), will be administrated for one cycle and safety and tumor assessment will be performed prior to drug administration on Cycle 4 Day 1.
- a) Dose de-escalation: if any DLT experienced before Cycle 3 Day 8, the dose will be de-escalated to Dose 3a (20 mg/m²) for Cycle 3 Day 8. If first DLT during Cycle 3 is experienced after Cycle 3 Day 8, the dose will be de-escalated to Dose 3a (20 mg/m²) for Cycle 3. If no DLT is observed in Dose 3a, the subjects will receive the Dose 3a until PD, consent withdraw or death. Once more dose de-escalation (Dose 3b, 16 mg/m²) will be allowed if another DLT is observed in Dose 3a.

Figure 2: Dose Modification

If the subject experienced any neurotoxic DLT, the subject will be withdrawn.

Subjects will be considered to be non-evaluable for ORR if they receive study drug for fewer than 9 weeks (3 cycles) of treatment for any reason other than study-drug related toxicity. Non-evaluable subjects will be replaced.

All subjects will be treated until the occurrence of progressive disease, intolerable adverse events (AEs)/toxicity, consent withdrawal or death. After discontinuation of study treatment, all subjects will be followed for survival and disease-specific therapies of the clinician's choice will be administered. Follow-up visits will be scheduled every 3 weeks for 9 weeks (i.e. week 3, week 6, and week 9), thereafter every 9 weeks until the end of the study.

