4.8. Selection and Timing of Dose for each Subject

The selection and timing of dose for each subject is described in [Section 3.1](#).

Subjects entered into Stage I and II will be allocated Dose 1, 2 and 3 under intra-subject dose escalation regimen. If the subject experiences a DLT at a given dose level, dose escalation will be halted and a reduced dose will be given to the subject. Dose adjustments were allowed based on the toxicity, efficacy evaluation, and clinical judgment by physician.

Dose 1: One i.v. administration of 12 mg/m² SCB01A on Days 1 and 8 of a Cycle 1;

Dose 1a: one i.v. administration of 9 mg/m² SCB01A
Dose de-escalation (if any DLT experienced during Dose 1)

Dose 1b: one i.v. administration of 7 mg/m² SCB01A
Dose de-escalation (if any DLT experienced during Dose 1a)

Dose 2: One i.v. administration of 18 mg/m² SCB01A on Days 1 and 8 of a Cycle 2;

Dose 2a: one i.v. administration of 15 mg/m² SCB01A
Dose de-escalation (if any DLT experienced during Dose 2)

Dose 2b: one i.v. administration of 12 mg/m² SCB01A
Dose de-escalation (if any DLT experienced during Dose 2a)

Dose 3: One i.v. administration of 24 mg/m² SCB01A on Days 1 and 8 of a Cycle 3;

Dose 3a: one i.v. administration of 20 mg/m² SCB01A
Dose de-escalation (if any DLT experienced during Dose 3)

Dose 3b: one i.v. administration of 16 mg/m² SCB01A
Dose de-escalation (if any DLT experienced during Dose 3a)

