4.9. Dose Adjustment and Toxicity Management

If a study treatment-related Grade 3 or 4 AE occurs, the study treatment will be placed on hold until the event is resolved to Grade ≤ 1 or returns to baseline before resuming the study drug. If the Grade 3 or 4 event does not resolve or return to baseline within 14 days or return to Grade 3 or 4 toxicity after resuming, treatment with the study drug will cease. However the subject should be followed-up for survival analysis until the end of the study.

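### For a DLT after Cycle 3 Day 8 or from Cycle 4 onward, Protocol sections 3.1, 3.2.11, 4.8 and 4.9 do not give one reconciled dosing instruction

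*Protocol*

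**What the plan says.** The dosing instructions are spread over several Protocol sections.

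- **3.1, general sentence (repeated in 4.8).** After a DLT at a given dose level, "dose escalation will be halted and a reduced dose will be given to the subject". No cycle is named. The next sentence adds: "Dose adjustments were allowed based on the toxicity, efficacy evaluation, and clinical judgment by physician". A neurotoxic DLT leads to withdrawal, and the documents do not contradict that.
- **3.1, item 3.** The 24 mg/m² step (Dose 3) is described as follows: it "will be administrated for one cycle and safety and tumor assessment will be performed prior to drug administration on Cycle 4 Day 1". Items 1 and 2 each carry a dose-maintained clause; for Dose 2 it reads "the Dose 2 can be continued until PD, intolerable toxicity, consent withdraw or death". Item 3 has no such clause. Its rule 3a covers a DLT before Cycle 3 Day 8 (20 mg/m² on that day) and a first DLT in Cycle 3 after Day 8 (20 mg/m², with Cycle 3 named as the cycle in which it is given). A further DLT at 20 mg/m² allows one more step, to Dose 3b (16 mg/m²).
- **3.2.11.** From Cycle 4, a subject with clinical benefit is covered by one phrase: "they may continue with treatment of SCB01A at the same dose until the study is terminated".
- **4.8.** Dose 3a is tied to the dose rather than the cycle: "Dose de-escalation (if any DLT experienced during Dose 3". The same section describes Dose 3 itself as Cycle 3 dosing.
- **4.9.** A treatment-related Grade 3 or 4 event brings this instruction: "the study treatment will be placed on hold until the event is resolved to Grade ≤ 1 or returns to baseline before resuming the study" (meaning SCB01A). The dose on resumption is not given. Treatment ceases if the event has not resolved or returned to baseline within 14 days, or if Grade 3 or 4 toxicity returns after resumption.
- **6.2.** A treatment delay of more than 14 days caused by drug-related toxicity is itself a DLT.

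In the Synopsis (efficacy criteria) and SAP section 9.8, only confirmed responses count towards the objective response rate (ORR). A subject whose response is not confirmed, or who is withdrawn for a DLT, is a non-responder.

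**The concern.** Section 3.2.11 is the only text written specifically for dosing from Cycle 4, and it does not say what happens after a DLT. The sections that do cover DLTs are either worded for Cycles 1 to 3 or do not state the resumed dose. In two situations, one section reduces the dose where another stops treatment. Two sites could therefore treat the same late DLT differently and each cite the Protocol.

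The first stake is patient safety. The second is interpretation. The period after Cycle 3 is when a first response is confirmed, and whether a subject is reduced, resumed or taken off treatment affects whether that subject can be counted as a responder. Dose adjustments are a safety endpoint (6.3), and DLTs and adverse events are tabulated by dose (8.4), so those tables would also reflect which section a site followed.

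**Working it through.** **Step 1. The instructions side by side, for non-neurotoxic DLTs at or after Dose 3.**

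| Event | 3.1 numbered rule | 3.1 general sentence and 4.8 | 3.2.11 | 4.9, if a related Grade 3-4 event |
|---|---|---|---|---|
| First DLT after Cycle 3 Day 8 | 20 mg/m², assigned to Cycle 3 | Reduced; 4.8 gives 20 mg/m² | Same dose, no exception | Hold, then resume at unstated dose |
| First DLT at 24 mg/m² in Cycle 4 or later | None | Reduced; 4.8 gives 20 mg/m² | Same dose, no exception | Hold, then resume at unstated dose |
| Further DLT at 20 mg/m², being Grade 3-4 toxicity that returns after resumption | 16 mg/m² allowed | Reduced; 4.8 gives 16 mg/m² | Same dose, no exception | Cease |
| Delay over 14 days from an unresolved related Grade 3-4 event | A DLT under 6.2, so as in the rows above | Reduced | Same dose, no exception | Cease |

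On the first row, infusions in Cycle 3 fall on Days 43 and 50 and the next is Cycle 4 Day 1 (Day 64). A DLT between Days 50 and 64 has no Cycle 3 infusion left to reduce. The parallel rules 1a and 2a name the following cycle (Cycle 2 and Cycle 3); rule 3a does not. Rules 1a and 2a are also worded for their own cycle, so a subject held at Dose 1 or 2 who has a first DLT in Cycle 4 or later meets the same gap.

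**Step 2. The no-DLT case.** Section 3.1 item 3 limits Dose 3 to one cycle and has no continuation clause. But Dose 2 also has the one-cycle phrase and is explicitly allowed to continue, so the phrase does not forbid continuation. Section 3.2.11 then supplies it: same dose. There is one answer.

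**Step 3. Dose difference between readings.** With two infusions per cycle, a first late DLT at Dose 3 gives 2 × 24 = 48 mg/m² per cycle under 3.2.11 taken alone and 2 × 20 = 40 mg/m² under 4.8. The difference is 8 mg/m² per cycle, or 8/48 = 16.7%. Under 4.9 the figure is not stated.

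**Step 4. Timing against confirmation.** The post-Cycle 3 scan is due at, or up to 4 days before, Cycle 4 Day 1, so on Days 60 to 64. Confirmation is at least 4 weeks later: 60 + 28 = Day 88 to 64 + 28 = Day 92. The infusions on Days 64, 71 and 85 (Cycle 4 Days 1 and 8, Cycle 5 Day 1) nominally come before the earliest confirmation scan. A DLT after any of them can fall before confirmation.

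**Step 5. Design figures.** The plan states 10 + 19 = 29 evaluable subjects, continuation with at least 1 of 10 responding, and success with at least 4 of 29. The exact probability of success is the sum over x = 1 to 10 of P(X₁ = x) × P(X₂ ≥ 4 − x), with X₁ ~ Bin(10, p) and X₂ ~ Bin(19, p). This gives 0.0468 at p = 0.05 (stated limit 0.05) and 0.8011 at p = 0.20 (stated power 0.80). Recruitment is 29/0.8 = 36.25, rounded up to 37. All agree with the plan, and none takes the dose after Cycle 3 as an input.

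**The case against.** The strongest reply is that the texts can be read together. Section 4.8 says that dose selection is described in 3.1, while 3.2.11 is a visit-schedule section with permissive wording. The general sentence in 3.1 names no cycle, and 4.8 ties Dose 3a to any DLT during Dose 3. On that reading, 3.2.11 means the same dose unless a DLT occurs, and 4.9 governs only holding and stopping. Rule 3a also goes on to say that Dose 3a continues if tolerated, which suggests dosing past Cycle 3. Physician judgment may change the dose in any case. Finally, the images of Figures 1 and 2 are not available, so they may show what the text omits.

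Much of this stands. It shows the sections are unreconciled rather than strictly incompatible. It does not settle the matter: nothing in 3.2.11 points to the DLT rules, rule 3a still names a cycle with no infusion left, and the last two rows of the table are real differences between reducing and ceasing.

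A reader might infer more than the documents support:

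- **That 3.2.11 keeps a subject on a dose that has just caused a DLT.** This takes one permissive sentence alone, against the reduction text in 3.1 and 4.8 and the hold in 4.9.
- **That every infusion after Cycle 3 is affected,** a share of (n − 3)/n: 25% with 4 cycles, 50% with 6, 67% with 9. This counts infusions in subjects without a DLT, for whom there is no conflict.
- **That every confirmation scan of a first response falls in Cycles 4 and 5.** Only the minimum interval is set, so Days 88 to 92 are the earliest dates and not a limit.

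**Conclusion.** The concern holds for a DLT after Cycle 3 Day 8 or in Cycle 4 and later. Sections 3.1 item 3, 3.2.11, 4.8 and 4.9 do not give one instruction for these events. It does not hold for a subject without a DLT.

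The size per affected subject is 48 against 40 mg/m² per cycle after a first late DLT at Dose 3, or a further reduction against stopping after a recurrent or unresolved Grade 3-4 event. The number of affected subjects is unknown because the documents give no rate of late DLTs. The effect on ORR cannot be computed either: it would need the share of responses lost because of the inconsistency, which the documents do not give. No bias in ORR is shown, and the sample size, error rate and power stand as stated.

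The point is still worth correcting. It bears on safety, and it affects treatment during a window in which three infusions nominally precede the earliest confirmation scan and withdrawal for a DLT makes a subject a non-responder. The conclusion rests on the text alone, since the two dosing figures could not be checked, and on nominal visit days.

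**What to change.** The sponsor's clinical team should reconcile 3.1 item 3 (including the cycle named in rule 3a), 3.2.11, 4.8 and 4.9, with the matching Synopsis text, so that they give one consistent instruction for a DLT after Cycle 3 Day 8 or in Cycle 4 and later. It should cover whether treatment is reduced, resumed or ceased, and how the 14-day provisions in 4.9 and 6.2 fit together. Section 3.2.11 should refer to it. Figures 1 and 2 should be checked against the result. No dose or clinical rule is proposed here.

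In the analysis, list for each responder the dose actually received from Cycle 4 onward. Protocol section 8.5 and SAP section 9.7.1.2 do not ask for this. The SAP is written in the past tense; if treatment has ended, this listing is the part that can still be acted on.

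The cost is a few sentences of amendment wording and one listing, with no extra subjects, visits or procedures.
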